#### D.8. Analysis Plan

**D.8.a. Primary Aim 1:** *Evaluate the predictive performance of the PDM, the QDRS, and the combined approach in the early detection of ADRD, compared to the gold standard diagnoses.*

For Primary Hypothesis 1, the screening approaches will be validated by evaluating the Area Under the Curve (AUC) for the PDM, the QDRS, and the combined approach. For the purpose of Aim 1, the PDM and the QDRS will be administered in the same sample of patients to increase power while retaining internal validity of conclusions. The AUC will be calculated from the plot of the sensitivity (y-axis) by 1 – specificity (x-axis) across all possible discrete screening score values. For the combined approach, screening will be considered positive if either PDM or QDRS are positive. The gold standard diagnosis will be determined as described in **D.7.a**. We hypothesize that the AUC, as well as the overall % accuracy of classifications, will be 0.85 or greater for the combined method, and 0.75 or greater for PDM and the QDRS.

For Secondary Hypothesis 2, dependent AUCs will be compared using the method that extends DeLong et al.'s nonparametric method to be valid for clustered data by using the Rao and Scott concepts for clustered binary data. The AUCs of different methods are dependent in the Aim 1 study because they are calculated on the same sample of patients. We hypothesize that the combined approach of PDM and QDRS will have statistically better AUC than PDM or the QDRS alone. In addition, the screening approaches will be compared on the overall % accuracy of classification (i.e., a simple proportion based on 0/1 data for each person) using nonlinear mixed models to account for correlated outcomes due to dependent methods and practice-clustered data.

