Potential problems & alternative strategies: The distributional assumptions for the binary outcomes are minimal, which will decrease the need to consider alternative analytic methods and models. However, to ensure the analytic methods appropriately account for the clustering effect when estimating standard errors and p-values, we will perform bootstrap estimation (i.e., using 1,000 datasets resampled with replacement at the person level) of the standard errors and confidence intervals surrounding the estimated values for AUC and % accuracy, and the estimated values for the difference in these values between screening approaches. In addition, if missing data occur, we will impute data using the simulation-based “Multiple Imputation” method, in which multiple complete datasets with plausible values for missing data are generated using model-based prediction, and analytic results from imputed datasets are aggregated to calculate appropriate standard errors and p-values in the presence of imputed data. We will use 100 imputed datasets, even though 10 to 50 are considered sufficient. Inclusion of potential auxiliary variables in the imputation model will be considered. A sensitivity analysis will be performed using participants with complete data.

**D.8.b. Primary Aim 2:** Evaluate the practical utility and effect of the PDM, and the combined methods in improving the annual rate of new documented ADRD diagnosis in primary care practices.

For Primary Hypothesis 1, three pragmatic screening approaches (AWV alone, AWV + PDM, and AWV + PDM + QDRS) will be compared on the annual incidence rate of EHR documented ADRD using nonlinear mixed models to account for clinic-clustered data. In the two pragmatic trials, different patients are randomized (via their clinics) to each of the 3 arms, making the outcomes independent between the three screening approaches; however, data will still be correlated for Aim 2 due to clustering of patients within clinics, which will be handled by random effects in the mixed models. We hypothesize the incidence rate will be 6% using AWV alone and 13% with the screening approach that combines AWV + PDM + QDRS. Incidence rates for all arms, including for AWV + PDM, will be calculated along with their 95% confidence interval.

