For Secondary Hypothesis 2, the analyses will be the same as described for Hypothesis 1 of Aim 2, except that the outcome will be acceptance rates for recommended ADRD diagnostic work-up following positive screen. We hypothesize the acceptance rate will be 44% using AWV alone and 66% with the screening approach that combines AWV + PDM + QDRS.

Potential problems & alternative strategies: Same as those described for Aim 1 above.

**D.8.c. Sample Size & Power:** Calculations were performed with PASS, a comprehensive power and sample size software. All calculations assume two-sided tests and alpha = 0.05. For study 1 (i.e., Aim 1), a sample size of 15 cluster pairs consisting of 400 persons (26.667 persons per cluster) will provide 81% power to compare population values of 75% versus 85% in the outcome of % accuracy of classification. This is based on using nonlinear mixed models to compare two paired (i.e., dependent) proportions. The proportions are considered dependent instead of independent because all three screening approaches for study 1 will be performed in the same sample of 400. This approach was selected because it will increase power by allowing participants to serve as their own controls. Moreover, it is appropriate for a diagnostic validity study to compare methods in the same sample (i.e., method contamination is not an issue). This calculation assumes that participants are recruited from 15 clinics (i.e., clusters) and that the within-pair coefficient of variation (CV) between clusters is .058. The CV was calculated as  $CV = \text{SQRT} (ICC \times (1 - \phi) / \phi)$ , where the intraclass correlation coefficient (ICC) was assumed to be 0.01, and phi is 0.75 (i.e. the proportion of accuracy for one of the standard screening methods). The power will be slightly greater than 81% to detect values of 75% versus 85% in the AUC, based on power for comparing two dependent AUC's, assuming discrete cutoff values, and accounting for a sample inflation factor (IF), where  $IF = [1 + (M - 1) * ICC]$ , M = average number of persons per cluster, and the ICC is 0.01.

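### The Aim 1 bootstrap is meant to allow for clustering but resamples persons: at the plan's ICC the SE of a single % accuracy is about 11% too small, while for AUCs and differences the shortfall may be nil

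*Combined protocol and SAP*

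**What the plan says.** The bootstrap appears in the potential-problems paragraph that follows D.8.a. Its purpose is "to ensure the analytic methods appropriately account for the clustering effect when estimating standard errors and p-values". Its specification is "we will perform bootstrap estimation (i.e., using 1,000 datasets resampled with replacement at the person level) of the standard errors and confidence intervals", and its targets are the quantities "surrounding the estimated values for AUC and % accuracy, and the estimated values for the difference in these values between screening approaches". It therefore covers single AUCs, single accuracies and the contrasts between approaches.

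The rest of the plan treats practices as clusters. In D.8.a, Secondary Hypothesis 2, accuracy is compared "using nonlinear mixed models to account for correlated outcomes due to dependent methods and practice-clustered data", which names the repeated tests and the practices as two separate sources of correlation. In the same place, AUCs are compared with an extension of the DeLong method intended "to be valid for clustered data by using the Rao and Scott concepts for clustered binary data". D.8.c takes 400 persons in 15 clinics, an ICC of 0.01 and an inflation factor of 1 + (M − 1) × ICC, and states that "the within-pair coefficient of variation (CV) between clusters is .058". D.2 lists 10 practices in Indianapolis and 10 in South Florida for all the studies.

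**The concern.** A bootstrap reproduces only the dependence carried by its resampling unit. When persons are drawn, each patient's set of test results stays together, so the dependence between tests survives. The correlation between patients of one practice does not. The step is thus introduced to handle clustering and then specified in a way that leaves out the practice part of it. No practice-level or two-stage bootstrap is described elsewhere.

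What is at stake is the precision reported for Aim 1. For a single AUC or a single % accuracy, this bootstrap is the only interval method that the plan names. For the comparisons, it is offered as a safeguard on methods that already allow for practices, yet it may show narrower intervals than they do for no good reason.

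**Working it through.** **1. Inputs.** From D.8.c: 400 persons, 15 clinics, M = 26.667, ICC 0.01, CV .058, accuracies of 75% and 85%, two-sided alpha 0.05. From D.2: 20 practices, hence M = 20. Within-person correlation, the sharing of practice effects between tests, and the share of cases are not in the documents and are assumed below.

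**2. The plan's own figures.** CV = sqrt(0.01 × 0.25/0.75) = 0.0577, which rounds to the stated value. The plan says that its sample "will provide 81% power to compare population values of 75% versus 85% in the outcome of % accuracy of classification". A matched-pair cluster formula gives

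z = sqrt{(15 − 2) × 0.10² / [0.1875/26.667 + 0.1275/26.667 + 0.058² × (0.75² + 0.85²)]} = sqrt(0.13/0.01614) = 2.838,

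and so power Φ(2.838 − 1.960) = 0.810. With CV = 0 the same formula gives 0.913.

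**3. Single % accuracy.** The ratio of person-level SE to practice-aware SE is 1/sqrt(IF), and coverage is 2Φ(1.96/sqrt(IF)) − 1.

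| Practices | IF | SE ratio | SE too small by | Coverage |
|---|---|---|---|---|
| 15 | 1 + 25.667 × 0.01 = 1.257 | 0.892 | 10.8% | 92.0% |
| 20 | 1 + 19 × 0.01 = 1.190 | 0.917 | 8.3% | 92.8% |

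At 85% accuracy the person-level half-width is 1.96 × sqrt(0.1275/400) = 3.50 points. Allowing for 15 practices it is 3.50 × 1.121 = 3.92, or 4.29 with t on 14 df. With 20 practices these become 3.82 and 4.08. If the ICC were between 0.005 and 0.05 (assumption), the shortfall would be 5.9% to 33.8% with 15 practices and 4.4% to 28.4% with 20.

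A simulation with 2,000 datasets of 400 persons in 15 clinics at ICC 0.01 agrees. At 75% accuracy the true SE was 0.0243–0.0245 against a person-level bootstrap SE of 0.0216, with coverage of about 91%.

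**4. Difference in % accuracy.** Let v1 = 0.1875, v2 = 0.1275 and c = sqrt(v1 × v2) = 0.1546. Let r be the within-person correlation and g the correlation of practice effects between the two tests. Per person, the bootstrap sees A = v1 + v2 − 2rc. The practice term it misses is B = 25.667 × 0.01 × (v1 + v2 − 2gc). The SE ratio is sqrt[A/(A + B)].

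- r = 0.3, g = 1: A = 0.2222, B = 0.0015, ratio 0.997 (about 0% too small).
- r = 0.3, g = 0.5: B = 0.0412, ratio 0.919 (8%).
- r = 0.3, g = 0: B = 0.0809, ratio 0.856 (14%).
- r = 0, g = 0: A = 0.315, ratio 0.892 (11%).

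A higher within-person correlation raises the upper end: r = 0.5 with g = 0 gives 0.815. In the simulation, drawn without within-person correlation beyond any shared practice effect, fully shared effects gave a true SE of 0.0279 against 0.0279, with 95% coverage. Independent effects gave 0.0313 against 0.0279, with 91% coverage.

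**5. AUC.** The combined approach is a yes/no rule: "For the combined approach, screening will be considered positive if either PDM or QDRS are positive". Its AUC is (sensitivity + specificity)/2. Assume both are 0.85, with ICC 0.01, n1 cases, n0 non-cases, and correlation h between practice effects on sensitivity and specificity. Then approximately

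SE ratio = 1/sqrt{1 + 0.01 × (2 + 2h)/[15 × (1/n1 + 1/n0)]}.

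| Case share (assumed) | h = −1 | h = 0 | h = 1 |
|---|---|---|---|
| 10% | 1.00 | 0.977 | 0.955 |
| 25% | 1.00 | 0.954 | 0.913 |
| 50% | 1.00 | 0.940 | 0.889 |

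Simulation (8,000 replicates) agrees to within about 0.01. The shortfall starts at zero and stays at or below about 5% when cases are few, because the variance then comes mostly from the small number of cases.

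**The case against.** The strongest reply is that little depends on this bootstrap. The comparisons under Secondary Hypothesis 2 already use cluster-aware methods. Primary Hypothesis 1 concerns AUCs, where the shortfall can be nil. The enrolled patients have no prior ADRD or MCI diagnosis, so the low case shares in the AUC table may be the relevant ones. All of this stands and sets the grade. It does not remove the mismatch between the bootstrap's stated purpose and its resampling unit.

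A second reply is that clustering might mean only several tests per patient, which person-level resampling does respect. D.8.a and D.8.c rule that out, since both name practices or clinics as clusters.

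Four stronger readings are tempting, and the documents do not support them.

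- *The 81% power proves that practice variation remains in the paired difference.* The match rests on one inferred formula, which treats the two tests as if done on different people. The plan names only its software and mixed models for paired proportions. A planning term does not show that practice effects fail to cancel. Moreover, CV .058 was derived at 75%; at 85% it implies an ICC of 0.058² × 0.85/0.15 = 0.019, not 0.01.
- *All Aim 1 intervals are too narrow.* A shortfall without further assumptions is shown only for single % accuracy.
- *A conclusion about 0.85 or 0.75 would change.* No rule in the plan sets an interval against these values.
- *Aim 2 is badly affected, because D.8.b carries over the Aim 1 strategies.* The bootstrap's named targets, AUC and % accuracy, are not Aim 2 outcomes, and D.8.b assigns clinic clustering to random effects.

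**Conclusion.** The contradiction is clear from the text: the resampling unit cannot carry the practice correlation that the plan assumes. At ICC 0.01, the SE of a single % accuracy is 10.8% too small with 15 practices and 8.3% too small with 20, which moves the half-width at 85% accuracy by about 0.4 points with 15 practices. For differences, the range is about 0% to 11%–14%, depending on how far practice effects are shared and on an assumed within-person correlation of 0 to 0.3. For AUCs, the effect is smaller, model-dependent and possibly zero. Confidence is high for the contradiction and for the single-accuracy figures. It is lower for differences and AUCs, which rest on assumptions that the documents do not fix. The point is minor.

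**What to change.** In D.8.a, take AUC intervals, both single and for differences, from the clustered AUC variance method already cited there. Take % accuracy intervals from the mixed model with a practice effect.

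If the bootstrap is kept, draw whole practices, with all their patients and all test results together. Do not use percentile limits. Use the bootstrap SE times sqrt(k/(k − 1)) with t on k − 1 df for k practices, with fewer df if resampling is stratified by health system (13 with 15 practices and two systems).

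The correction matters. In a simulation of single accuracy with 15 practices at ICC 0.01, practice-level percentile intervals covered 91.9% at both 75% and 85%, no better than person-level ones (91.9% and 92.8%). The corrected intervals covered 94.7% and 94.6%. For a graded AUC of 0.85 with 10% cases, the corrected interval reached only 92.8%–93.3%, against 91.6%–92.4% for the person-level normal interval. For AUC, the clustered variance method should therefore be primary.

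The cost is about one sentence in D.8.a and trivial programming. The downside is slightly wider intervals: at 85% accuracy, 3.5 points become 3.9, or 4.3 with t on 14 df. Aim 2 needs no change. An optional note in D.8.b could say that the person-level bootstrap does not carry over.

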In response to the RFA-AG-20-051 call for the "validation, and translation of screening and assessment tools for measuring cognitive decline," our interdisciplinary scientific team is proposing to execute a clinical validation study, one pragmatic trial and one additional replicated pragmatic trial among patients from diverse rural, suburban and urban primary care practices in two independent sites located in central Indiana and south Florida. As required by the RFA, the first study will be a single-arm clinical validation (NIH Stage III) study of our developed early ADRD detection approaches; Passive Digital Marker (PDM) and the Patient Reported Outcome (PRO) tool, the Quick Dementia Rating System (QDRS) for discriminating gold standard ADRD diagnoses for a sample of 400 older primary care patients served in the two states. The other studies will be two pragmatic cluster-randomized controlled comparative effectiveness (NIH Stage IV) trials to incorporate the PDM and the QDRS within the Medicare paid Annual Wellness Visit (AWV) for a cohort of patients from practices across the two independent sites, with practices randomized in each pragmatic trial to one of the 3 arms (the AWV alone, the AWV with PDM, and the AWV with both the PDM and the QDRS).

These studies will support the following aims:

**Primary Aim 1:** Evaluate the predictive performance of the PDM, the QDRS, and the combined (PDM + QDRS) approach in the early detection of ADRD, compared to the gold standard diagnoses.

*Primary Hypothesis 1:* The Area Under the Curve (AUC) for the combined approach (PDM + QRDS) will be 0.85 or greater and the AUC for the PDM or the QDRS will be 0.75 or greater.

*Secondary Hypothesis 2:* The combined approach (PDM + QDRS) will have statistically better AUC than each individual approach alone.

**Primary Aim 2:** Evaluate the practical utility and effect of the PDM, the QDRS, and the combined approach (PDM + QDRS) in improving the annual rate of new documented ADRD diagnosis in primary care practices.

*Primary Hypothesis 1:* In comparison to the AWV alone, the combined approach (PDM + QDRS) within the AWV will increase the incidence rate of ADRD over the subsequent 12 months from 6% to 13%.

*Secondary Hypothesis 2:* In comparison to the AWV alone, the combined approach (PDM + QDRS) within the AWV will have higher acceptance rates for recommended ADRD diagnostic work-up following a positive screen from 44% to 66%.

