**A. SIGNIFICANCE: Our proposal is designed to help clarify the following important questions.**

**A.1. What is the value of early detection of Alzheimer Disease and Related Dementias (ADRD)?** Primary care clinicians provide the vast majority of care to older adults living with ADRD. However, more than 50% of these older adults never receive a formal diagnosis. And for those patients who are diagnosed with ADRD, the diagnosis often occurs 2-5 years after symptom onset when the syndromes reach mild to moderate stage. The inability to diagnose ADRD and manage its cognitive, functional, and psychological disabilities results in significant burden for patients, families, and the entire society. Early detection of ADRD could reduce this burden. Furthermore, early detection will become increasingly important for ensuring that people receive early ADRD disease modification treatment when available. Thus, the National Academy of Sciences, National Plan to Address Alzheimer's Disease, and Affordable Care Act all describe earlier ADRD detection as a core aim for improving the quality of care for older adults.

**A.2. Can the Annual Wellness visit (AWV) overcome barriers for early detection of ADRD?** Beginning in 2011, the Centers for Medicare and Medicaid Services (CMS) started paying providers (with no patient requirement for copayment) for the AWV. Although the AWV does not mandate formal ADRD screening, the beneficiary's cognitive function is assessed through direct observation, potentially supplemented with information provided by family members. In 2018, we published the results of a study that evaluated the ability of the current format of the AWV to improve ADRD detection. Using de-identified administrative claims data for a nationally representative sample of Medicare beneficiaries, we found no impact for the AWV in its current format on the diagnostic rate, testing, or care management for ADRD. Enhancing the AWV with integrated scalable formal screening will likely facilitate earlier identification of ADRD.

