**D.4. Primary Care Practices Recruitment into the Pragmatic (Phase IV) Trials:** We will approach the practice manager and the physician leader of each primary care practice to randomize their site into one of three early detection approaches; AWV and any other visit to the primary care physician or geriatrician without PDM or QDRS; AWV and any other visit to the primary care physician or geriatrician with PDM; and AWV and any other visit with the primary care physician or geriatrician with both PDM and QDRS. We have received approval from the leadership of both Eskenazi Health and UHealth. The PDM and the QDRS will be embedded within the AWV process for each practice. The current rate of using the AWV across the country is increasing from 14% in 2012 to more than 60% in our own practices. We will obtain a waiver of informed consent from the local Institutional Review Board to review retrospectively (after at least one year of screening) the EHR systems of each practice to calculate the annual rate of new ADRD diagnosis and other EHR data to measure processes of diagnostic assessment following the AWV including screening rate, referral rate for diagnostic assessments for early ADRD and patient acceptance rate of undergoing such assessments. In addition, we will interview the practice managers by implementing a one-time completion of Practice Transformation Assessment (PTA) for each clinic enrolled in the pragmatic trial at Eskenazi Health and University of Miami Health. This will be administered by the RA or Project Manager and completed by the Practice Manager. It will be variable, we will integrate it into our research method to describe the context of our healthcare system participating in our research. We want to know if there is any difference in the results between University of Miami Health (UMiami) and Eskenazi Health, and if that is related to different practice variable specifically the payment and healthcare transformation.

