**D.6. Integrating the PDM and QDRS within the Epic EHR:** We will leverage the processes and technologies currently and successfully in use every day in our clinical partner's primary care practices. These practices at both sites use Epic as their EHR and its related computerized decision support (CDS) engine and its patient-completed survey platforms. As indicated in the preliminary studies, EHRs contain detailed clinical data that can be accessed to run the PDM algorithm. EHRs also have a platform for patient reported outcome (PRO) survey in which we will integrate the QDRS for the selected primary care practices. The EHR-based CDS system will display the results of the screening to clinicians to promote the interpretation of the results by healthcare providers and patients. The Regenstrief Institute (see Resources section) has decades of experience in successful CDS research and implementation. Over the past three years, we have partnered with our Epic EHR clinical informatics colleagues to deploy various CDS tools such as patient reported surveys, predictive algorithms for social frailty, and deprescribing recommendations. These CDS tools provide clinicians with a graphical summary of the results with a focus on the factors driving these results. A similar approach will be adopted in this study, tailored through the extensive configuration options available in the Epic CDS engine. Patient registration at the primary care clinic would trigger the CDS process including patient completion of the QDRS. The CDS engine will also query the data sources for the required input features specific to the patient and invoke the PDM ML algorithm. Results will be displayed within the EHR user interface with an emphasis on the key features of the model that explain the final outcome for each individual patient, including actionable clinician-directed recommendations related to appropriate diagnostic work-up. The proposed workflow will be deployed in the two healthcare systems (Eskenazi Health and UHealth) and integrated within the flow of the primary care practices. We have received the approval from leadership at both sites for the deployment of both the PDM and the QDRS, as described in their letters of support. The technical infrastructure (including servers, EHR and CDS configuration options, and data connections) as well as the security and governance agreements already exist and therefore pose no threats to project objectives or risk of delayed timelines.

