#### **D.7.b. Incidence of ADRD for the pragmatic cluster-randomized comparative effectiveness clinical trials:**

For the two pragmatic trials and using similar approach from previous studies, we will use data captured by the EHR to assess for two outcomes. The primary outcome measure will be any new ADRD case identified (documented in the EHR) within 12 months of the Annual Wellness Visit (index visit). The secondary outcome measures will be any services related to cognitive diagnostic assessment in the post Annual Wellness Visit (index) period that providers may order to diagnose or exclude ADRD. Specifically, the metrics

of diagnostic assessment will be evaluated as proportions of patients with a record of 1 or more of:

- Laboratory tests for TSH, serum B12, folate, or syphilis; individually or combined at any point during the 90 days after index
- Neuropsychological testing, including testing by psychologist or physician, technician administrator, computer, or other providers during the 12 months after index date
- Brain imaging testing (computed tomography, magnetic resonance imaging, positron emission tomography, magnetic resonance angiogram) of the head and neck, brain, or skull during the 12 months after index date
- Medications approved for management of ADRD (cholinesterase inhibitors, memantine) during the 12 months after index date

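### Aim 2 Secondary Hypothesis 2 compares acceptance after a positive screen with an AWV-alone arm that has no rule for a positive, and its 99% power counts all patients rather than screen-positives

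*Combined protocol and SAP*

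**What the plan says.** The Specific Aims state that, compared with AWV alone, the combined approach "will have higher acceptance rates for recommended ADRD diagnostic work-up following a positive screen from 44% to 66" per cent. D.8.b keeps the Hypothesis 1 mixed model "except that the outcome will be acceptance rates for recommended ADRD diagnostic work-up following positive screen", and adds: "We hypothesize the acceptance rate will be 44% using AWV alone", citing the earlier dementia screening trial (reference 17).

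D.4 defines the control arm as "AWV and any other visit to the primary care physician or geriatrician without PDM or QDRS". D.5 describes it as the AWV as currently practised. Section A.2 says that "the AWV does not mandate formal ADRD screening" and that cognition is judged by direct observation, possibly with information from family.

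The only rule for combining the tools (positive if either one is) appears in D.8.a, for Aim 1. The QDRS score bands in C.5 need a completed QDRS. D.8.b, E and F call AWV alone a screening approach or mention patients who screened positive, but give no rule.

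On data, D.4 plans to extract "screening rate, referral rate for diagnostic assessments for early ADRD and patient acceptance rate of undergoing such assessments". D.7.b instead says: "The secondary outcome measures will be any services related to cognitive diagnostic assessment in the post Annual Wellness Visit (index) period", and lists laboratory tests, neuropsychological testing, brain imaging and ADRD medication as proportions of patients.

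D.8.c gives 99% power for acceptance under both recruitment scenarios. Its footnote bases all pairwise power on 866 or 1,200 patients and five clusters per arm.

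**The concern.** The outcome exists only for patients with a positive screen and a recommended work-up. In the combined arm the tools can supply positives. In control, the plan describes what happens at the visit but not how it becomes a positive.

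If each arm identifies positives in its own way, the two denominators contain differently selected patients. A group picked out by a clinician's observation may differ in severity, and in readiness for work-up, from a group flagged by an algorithm or questionnaire. Acceptance could then differ with no effect of the intervention on acceptance, or a real effect could be hidden. Randomising practices does not protect a comparison conditioned on an event that the intervention itself helps to create.

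The 99% power figure also suggests that this comparison is secure, when it was calculated on a different and larger denominator.

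**Working it through.** **Inputs from the plan.** Two-sided alpha 0.05; acceptance 44% v 66%; ICC 0.01; five clusters per arm; N = 866 (M = 173.2) or 1,200 (M = 240) per arm; inflation factor 1 + (M − 1) × ICC (all D.8.b and D.8.c).

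**Assumption.** q, the share of patients who screen positive. The plan does not give it, so a range is shown.

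**Formulas.** n = N × q per arm; M = n/5; DE = 1 + (M − 1) × 0.01; V = sum over arms of p(1 − p) × DE/n; d = |p2 − p1|/√V. Power on the normal reference is Φ(d − 1.960). The t version uses a noncentral t with 10 − 2 = 8 df and noncentrality d.

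**Step 1: reproduce the plan's table with all patients (q = 1).**
- Incidence 6% v 13%, N = 866: DE = 1 + 172.2 × 0.01 = 2.722; V = (0.0564 + 0.1131) × 2.722/866 = 0.000533; d = 0.07/0.02308 = 3.03; power 85.8% (stated 86%).
- Incidence, N = 1,200: DE = 3.390; d = 3.20; power 89.2% (stated 89%).
- Acceptance 44% v 66%, N = 866: V = (0.2464 + 0.2244) × 2.722/866 = 0.001480; d = 0.22/0.03847 = 5.72; power above 99.9% (stated 99%).
- Acceptance, N = 1,200: d = 6.03; power above 99.9% (stated 99%).

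The method matches the incidence entries, and the footnote applies the same full arms to acceptance. No reduction to screen-positives was made.

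**Step 2: count screen-positives only, equal q in both arms.** V = 0.4708 × DE/n.

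| N per arm | Assumed q | n per arm | DE | d | Power, normal | Power, t (8 df) |
|---|---|---|---|---|---|---|
| 866 | 5% | 43.3 | 1.077 | 2.03 | 53% | 43% |
| 866 | 10% | 86.6 | 1.163 | 2.77 | 79% | 68% |
| 866 | 20% | 173.2 | 1.336 | 3.65 | 95% | 89% |
| 866 | 30% | 259.8 | 1.510 | 4.21 | 99% | 96% |
| 1,200 | 10% | 120 | 1.230 | 3.17 | 89% | 79% |
| 1,200 | 20% | 240 | 1.470 | 4.10 | 98% | 95% |

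**Step 3: unequal shares (also assumed), N = 866.** With 5% positive in control and 20% in the combined arm, power is 70% (normal) or 59% (t). With 10% and 30% it is 90% or 81%.

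**Step 4: screen-positives needed per arm.** Because DE/n = 0.99/n + 0.002, 99% power on the normal reference needs V = (0.22/4.286)² = 0.002635. Then 0.99/n = 0.002635/0.4708 − 0.002 = 0.003597, so n is about 275. On t with 8 df it is about 446. These are 32% and 52% of 866, or 23% and 37% of 1,200. For 80% power the need is about 89 (normal) or 123 (t).

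**The case against.** The strongest reply is that the control arm is not a blank. A.2 describes cognitive assessment by direct observation, and D.5 defines control as the current AWV. A clinician can suspect impairment and recommend a work-up, and the patient can accept or decline. A reader might infer that control patients can never screen positive; the documents do not support that. What stands is narrower: no rule turns that observation into a recorded positive.

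A common rule is also conceivable. D.6 says "The CDS engine will also query the data sources for the required input features specific to the patient and invoke the PDM ML algorithm", so the PDM could in principle be scored in every arm. The plan does not say that it will be, and this would not cover positives found by the QDRS.

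A reader might infer that acceptance was never a planned outcome, because D.7.b omits it. D.4 and D.8.c both name it, so this is a misalignment between sections.

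A reader might also infer that the 44% is wrong. It is presented as a hypothesis with a citation, and the cited report is not available here. C.3 shows only that the cited trial used formal screening tests and referred those positive, which is a different setting from AWV alone.

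Finally, every share in the working is assumed, and the normal reference is optimistic with ten clusters, which is why the t figures stand beside it. Five clusters per arm and the patient counts are taken from D.8.c as given.

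**Conclusion.** Both parts hold. The denominator for AWV alone has no rule. If positives arise by different means in each arm, 44% v 66% cannot be read as a randomised effect. The 99% power is correct arithmetic on the wrong denominator, so it is unsupported for this outcome.

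The size depends on a share the plan does not state. At 866 per arm with equal shares, power runs from 68–79% at 10% positive to 89–95% at 20%, and 99% needs about a third to a half of each arm to be positive. A reader might infer that the comparison must be underpowered. The documents do not show that: with a large and similar yield in both arms, power would still be high.

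This concerns a secondary hypothesis, and the primary incidence outcome is not affected by this point. It should be corrected before the Aim 2 data are retrieved, so that the denominator is not chosen with results in view.

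**What to change.** 1. Remove the two 99% entries in D.8.c, or restate them on the expected number of screen-positives, with the share given as an assumption for each arm and a t reference suited to ten clusters.
2. Make the randomised between-arm test an outcome measured in all index-visit patients: one pre-named work-up metric from D.7.b, with its stated window, in the same mixed model. Align the Specific Aims, D.7.b and D.8.b.
3. Keep acceptance among screen-positives as a descriptive measure. State the positive rule for each arm, and note that the groups are selected after randomisation.
4. Say that the 44% comes from a trial with formal screening tests and is an assumption for AWV alone.

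**Cost.** No new data source is expected: D.7.b already takes these services from the EHR, and D.4 already plans to extract acceptance. The question changes, because a work-up metric measures services ordered rather than acceptance, and background testing of the kind reported in C.2 may dilute it. The stated power also becomes less favourable. As a guide, at 866 per arm, 80% power and an assumed 10% control rate, the detectable increase is 7.6 points (normal) to 8.9 (t) at ICC 0.01, 10.0 to 11.7 at ICC 0.02, and 15.6 to 18.3 at ICC 0.05. The control rate and ICC for the chosen metric should be labelled as assumptions.
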